9 SUBJECT MANAGEMENT

9.1 Subject Follow-up

9.1.1. In home assessments.

Participants will complete an at-home symptom questionnaire by REDcap on each day of follow-up through day 28, including in-home assessments of temperature and O2 saturation. These assessments will be reviewed daily by a clinical research coordinator, and patients will be telephoned by a physician if they report an elevated temperature, diminished O2 sat (<94%), or signs/symptoms of respiratory or cardiopulmonary distress (e.g. shortness of breath, dyspnea on exertion). On each day through day 28, patients will also be instructed to collect an anterior nare swab in a pre-labeled container and to store these specimens in a refrigerator at 2°C to 8°C, and to bring these in to their next scheduled appointment. Prior to the optional follow up visits at months 4, 7 and 10, participants will complete an at-home symptom questionnaire and will be asked to collect a stool specimen to bring to their next scheduled appointment.

9.1.2. Follow-up in-clinic assessments.

[figure not shown]
Participants will be seen at follow-up visits at Day 1±1, 3±1, 5±1, 7±1, 10±1, 14±1, 21±1, and 28±1. At each visit, a subjective medical history will be performed, including assessments for use of any concomitant medications. Vital signs will be obtained (temperature, blood pressure, pulse rate per minute, breath rate per minute and oxygen saturation), and oropharyngeal and anterior nare swabs will be collected. Participants will also submit at-home collected anterior nare swab specimens for evaluation. Clinical laboratory measurements will be performed at days 5±1 and 14±1 to assess for safety, with additional clinical laboratory assessments performed as needed for clinical follow-up and/or patient management. Additionally, ~25 mL peripheral blood will be collected from study participants at enrollment and at Days 5±1, 14±1, and 28±1 for processing and cryopreservation into a specimen biobank. Safety and tolerability of Lambda will be assessed by adverse event (AE) monitoring, vital signs assessment and clinical laboratory tests. Patients will reach the end of study at day 28±1 of follow-up. Optional long-term follow up visits will be scheduled 4, 7, and 10 months post-enrollment. The window of ±3 weeks is allowed for these long term follow up visits.

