Area under the curve (AUC) will be defined by a single participant's logarithmic base 10 viral load from oropharyngeal tests collected on days 0, 1, 3, 5, 7, 10, and 14. AUC will be calculated by the trapezoidal rule, using exact times of collection of each OP swab. Multiple imputation using chained equations will be used to impute missing viral load data prior to AUC calculation. Five data sets will be imputed, and imputed values will be calculated using non-missing viral load on each of the 7 sample collection days, treatment arm, age, sex, and whether or not a participant was hospitalized. A pooled linear regression model will be fit to log-transformed AUC as a function of treatment, age, and sex using the 5 imputed data sets. Difference in AUC by treatment arm and corresponding 95% confidence intervals will be reported using Rubin's Rules. The difference in AUC by treatment arm will also be done after refitting the model without participants who were hospitalized to assess sensitivity of results.

The incidence of hospitalizations and emergency department visits will be estimated for each arm, with 95% confidence intervals.

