## 3 HANDLING OF MISSING AND CENSORED DATA

All efforts will be made to minimize instances of missing data. However, we expect some missing data will occur. Our analyses will assume data are missing at random. For the primary endpoint of time to shedding cessation, any participant who drops out prior to having two consecutive negative tests will be censored at their last positive test. Participants who have no post-randomization test results available or a single test result that is negative will be censored at day 1. Similarly, participants will be right censored for the time to symptom resolution or progression at the time when their last symptom questionnaire is completed. Participants who are asymptomatic at screening and never report symptoms thereafter will be considered to have met symptom resolution at study Day 1. For other missing data, we will use multiple imputation-based analyses. This approach will be applied to any analysis involving endpoints or key

variables where any missing data occurs in order to adhere to the ITT principle. Sensitivity to assumptions regarding missingness will be addressed through sensitivity analyses.

If more than 5% of participants do not have the time of shedding cessation observed (i.e. they are right-censored), we will perform a sensitivity analysis to evaluate the robustness of our findings to missing data assumptions. In the sensitivity analysis, among those missing timing of shedding cessation, we will assume varying proportions (e.g. 25%, 50%) of participants in each arm who would have ceased shedding by Day 28. The proportions will differ by arm so we can evaluate whether our findings stand if it were true that people who dropped out stopped shedding earlier in the placebo arm vs the active arm.

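### Five imputations with no stated seed leave avoidable Monte Carlo error in the secondary oropharyngeal viral-load AUC; it matters only for results near p = 0.05

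*SAP*

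**What the plan says.** SAP 1.3 lists oropharyngeal viral-load AUC through Day 14 as a secondary endpoint. SAP 2.4 builds it from each participant's "logarithmic base 10 viral load from oropharyngeal tests collected on days 0, 1, 3, 5, 7, 10, and 14". For gaps in that series, "Multiple imputation using chained equations will be used to impute missing viral load data prior to AUC calculation". The number of imputations and the first predictors follow: "Five data sets will be imputed, and imputed values will be calculated using non-missing viral load on each of the 7 sample collection days". The other predictors are "treatment arm, age, sex, and whether or not a participant was hospitalized". In that paragraph viral load means oropharyngeal load, and no nasal variable is listed.

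The analysis is then specified: "A pooled linear regression model will be fit to log-transformed AUC as a function of treatment, age, and sex". For reporting, "Difference in AUC by treatment arm and corresponding 95% confidence intervals will be reported using Rubin's Rules". SAP 2.2 sets alpha at 0.05 for all tests unless otherwise noted.

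SAP 2.5 plans similar approaches for nasal AUC. SAP 3 extends multiple imputation to other missing data ("This approach will be applied to any analysis involving endpoints or key" variables) but gives no number of imputations there. I found no analysis seed, no reason for choosing five, and no check of Monte Carlo error. The planned sensitivity analyses, which are a refit without hospitalised participants (SAP 2.4) and a variation of the missingness assumptions (SAP 3), do not address the number of imputations.

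**The concern.** With a finite number of imputations, two analysts who follow the SAP exactly on the same locked data, but with different seeds, will get slightly different estimates, intervals and p-values. With five imputations and no fixed seed, that difference can carry a borderline AUC result across 0.05. What is at stake is the stability of one secondary result when it falls close to the line. A seed chosen after unblinding would also leave an analyst discretion that one sentence could remove.

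**Working it through.** **Inputs from the documents.** m = 5 imputations (SAP 2.4); alpha 0.05 (SAP 2.2); 120 patients, 60 per arm (SAP 1.1); 90% expected to complete follow-up (Protocol synopsis). The documents give no missing-swab rate, SD or effect size for AUC, so there is no stated figure to reproduce.

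**Assumed.** Fraction of missing information (FMI) about 5%, with 10% as a higher case; a result at z = 2.0; two-sided normal p-values.

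**Seed-only spread.** Let B be the between-imputation variance and T the total variance. The seed-only variance of the pooled estimate is B/m. Since FMI is approximately (1 + 1/m)B/T,

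SD of z across seeds = sqrt(FMI / [(1 + 1/m) × m]) = sqrt(FMI / (m + 1)).

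| FMI | m | SD of z | 95% seed range of z | 95% seed range of p |
|---|---|---|---|---|
| 5% | 5 | sqrt(0.05/6) = 0.091 | 1.82 to 2.18 | 0.029 to 0.069 |
| 5% | 50 | sqrt(0.05/51) = 0.031 | 1.94 to 2.06 | 0.039 to 0.053 |
| 10% | 5 | sqrt(0.10/6) = 0.129 | 1.75 to 2.25 | 0.024 to 0.081 |
| 10% | 50 | sqrt(0.10/51) = 0.044 | 1.91 to 2.09 | 0.037 to 0.056 |

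**Is 5% plausible?** Simulations of 120 patients used the SAP's seven visits and imputation predictors, with 10-15% drop-out and 0-20% missed single visits assumed. In the main settings FMI was about 2-6%. With noisier within-person measurements it was 7-14%. Loads were taken as non-negative on the log10 scale and AUC was floored at 1 in the flip-rate runs below, because the Ct conversion printed in SAP 2.4 gives a log10 load of zero or below for any Ct up to 42. The formula above does not depend on that choice.

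**How often a verdict changes.** For trials whose many-imputation p-value is 0.04, the share reported at p ≥ 0.05 because of the seed alone was:

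| Specification | Main settings | Noisier settings |
|---|---|---|
| m = 5, as written | 9-21% | 26-38% |
| m = 20 | 1-4% | 6-19% |
| m = 50 | about 0% | 0-5% |
| m = 5 plus same-day nasal load | 8-20% | 21-36% |

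The m = 50 row is slightly optimistic because sets were drawn from a finite pool. At a reference p of 0.02, 0.2% or fewer changed at m = 5 in the main settings.

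**Averaged over where z might fall.** The chance that m = 5 and unlimited imputations disagree at 0.05 is roughly the density of z at ±1.96 times the mean absolute seed error, 0.798 × SD. At FMI 4-6% the SD is sqrt(0.04/6) = 0.082 to sqrt(0.06/6) = 0.100.
- Under the null: 2 × 0.0584 × 0.798 × SD = 0.8-0.9%.
- With expected z = 2: 0.3986 × 0.798 × SD = 2.6-3.2%.

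**Nasal load as an auxiliary predictor.** Protocol 9.1.1 says "patients will also be instructed to collect an anterior nare swab in a pre-labeled container" on each day through day 28, so a same-day nasal value can exist when one clinic swab is missed. Home swabs are handed in at the next visit, so most are lost after drop-out. Adding the nasal load shortened the standard error by about 0.4-2.6% in the main settings and 1-5% in the noisier ones, under assumed same-day correlations (0.3-0.85 across the runs). At m = 5 it moved the p = 0.04 flip rate from 9.4% to about 8% with drop-out alone, and from 21% to 12-20% with 15% missed visits.

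**The case against.** The strongest defence is that five imputations are not an error. Rubin's Rules carry the (1 + 1/m) term for finite m. At 5% missing information the relative efficiency is 1/(1 + 0.05/5) = 99%, which is a standard-error inflation of sqrt(1.01) − 1, or about 0.5%. No bias or loss of coverage follows. SAP 2.4 promises a difference with a 95% interval for AUC and names no AUC p-value, and no decision in the trial depends on one. SAP 3 handles the primary endpoint by censoring. All of this stands, and it is why the point is small.

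Three stronger readings are tempting, and the documents support none of them.

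- A reader might infer that the AUC result cannot be reproduced. A saved seed reproduces it exactly, and the SAP is silent on a seed; it does not say that none will be kept.
- A reader might infer that omitting nasal data makes results flip. The number of imputations drives the flipping: raising m to 50 alone nearly removes it in the main settings, while adding nasal load at m = 5 changes it little. No document gives the oropharyngeal-nasal correlation, and joint imputation would double the viral-load variables in a model for 120 patients.
- A reader might infer that five applies to every imputed analysis. SAP 3 states no number.

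What the defence leaves unanswered is that the seed-only spread near 0.05 is real and costs almost nothing to remove.

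**Conclusion.** The point holds as a minor improvement. SAP 2.4 fixes five imputations without a seed, so the pooled AUC estimate carries Monte Carlo error of about 0.09 standard errors at 5% missing information, against about 0.03 with 50 imputations. Only results near 0.05 are exposed, and averaged over possible results the verdict would change in about 1-3% of trials at 4-6% missing information. The analysis is valid as written and the primary Cox analysis is untouched. The sizes rest on assumed missingness and measurement noise. Missing information above the simulated range, such as 20%, would widen the seed range further, but nothing in the documents or the simulations (highest average about 14%) points to it.

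**What to change.** In SAP 2.4, replace five with at least 50 imputed data sets, pre-specify the seed, and report the Monte Carlo error of the pooled AUC difference. In SAP 3, state that the same number applies wherever multiple imputation is used. A seed alone would make the result repeatable but still arbitrary, so the number of imputations is the part to change first.

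Optionally, add the same-day anterior-nares log10 load, imputed jointly, as an auxiliary predictor, after checking that the chained-equation model remains stable with the extra variables. Expect only a small gain in precision.

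The core change costs a sentence or two in the SAP and minutes of computing. It needs no new data, visits or patients.

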3.2. Secondary objectives

- To evaluate the efficacy of subcutaneous injection of a single dose of 180 mcg of Peginterferon Lambda-1a compared with placebo, in reducing the duration of symptoms, hospitalizations, or ED visits in patients with uncomplicated COVID-19 disease.
- To evaluate the safety and tolerability of subcutaneous injection of a single dose of 180 mcg of Peginterferon Lambda-1a compared with placebo.

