6.3 Exclusion Criteria

1. Patients who are hospitalized for inpatient treatment or currently being evaluated for potential hospitalization at the time of initiation of informed consent
2. Patients with a known allergy to Peginterferon Lambda-1a or any component thereof

3. Display symptoms of respiratory distress (Respiratory rate >20, room air oxygen saturation of <94%).
4. Participation in a clinical trial with or use of any investigational agent within 30 days before screening
5. Treatment with interferons (IFN) within 12 months before screening
6. Previous use of Peginterferon Lambda-1a
7. History or evidence of any intolerance or hypersensitivity to IFNs or other substances contained in the study medication.
8. Female patients who are pregnant or breastfeeding. Male patients must confirm that their female sexual partners are not pregnant.
9. Current or previous history of decompensated liver disease (Child-Pugh Class B or C) or hepatocellular carcinoma
10. Co-infected with human immunodeficiency virus (HIV)
11. Any of the following abnormal laboratory test results at screening:
 - a. Platelet count <75,000 cells/mm³
 - b. Absolute neutrophil count <800 cells/mm³
 - c. Hemoglobin <11 g/dL for women and <12 g/dL for men
 - d. Serum creatinine concentration $\geq 1.5 \times$ ULN and creatinine clearance (CrCl) < 50 mL/min by Cockcroft-Gault
12. History of liver disease other than viral hepatitis
13. Prior history or current evidence of any of the following:
 - a. Immunologically mediated disease that is uncontrolled
 - b. Retinal disorder or clinically relevant ophthalmic disorder
 - c. Any malignancy (excluding non-melanoma skin cancer) within 5 years before screening
 - d. Cardiomyopathy or significant ischemic cardiac or cerebrovascular disease.
 - e. Chronic uncontrolled pulmonary disease
 - f. Pancreatitis
 - g. Severe or uncontrolled psychiatric disorder
 - h. Active seizure disorder
 - i. Bone marrow or solid organ transplantation
14. Other significant medical condition that may require intervention during the study
15. Concurrent use of any of the following medications:
 - a. Therapy with an immunomodulatory agent
 - b. Current use of heparin or Coumadin
 - c. Received blood products within 30 days before study randomization
 - d. Use of hematologic growth factors within 30 days before study randomization
 - e. Systemic antibiotics, antifungals, or antivirals for treatment of active infection within 24 hours before study randomization

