### 1.3 Secondary endpoints

Secondary endpoints include the following:

- Time until resolution of all symptoms;
- SARS-CoV-2 viral load over time in oropharyngeal tests;
- SARS-CoV-2 viral load area under the curve in oropharyngeal tests through Day 14;
- Number of emergency department visits or hospitalizations within 28 days of treatment.

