# 2 ANALYSIS PLAN

## 2.1 Analysis populations

The intent-to-treat (ITT) population will include all randomized patients. Patients will be analyzed according to their assigned treatment arm. All efficacy analyses will be completed in the ITT population.

The as-treated population will include all randomized patients. Patients will be analyzed according to the treatment actually received.

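### The one AUC sensitivity analysis the SAP sets out drops hospitalised participants, so it is not a randomised comparison and does not vary the missing-at-random assumption; the likely distortion is small.

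*SAP*

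**What the plan says.** **AUC analysis (SAP 2.4).** The AUC is built from log10 oropharyngeal loads on Days 0, 1, 3, 5, 7, 10 and 14. On missing loads: "Multiple imputation using chained equations will be used to impute missing viral load data prior to AUC calculation". Five data sets are imputed, using the observed loads on the seven days plus "treatment arm, age, sex, and whether or not a participant was hospitalized". Log-transformed AUC is then regressed on treatment, age and sex and pooled by Rubin's rules. Hospitalised participants therefore stay in the main analysis.

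**Sensitivity analysis (SAP 2.4).** The arm difference is obtained again after "refitting the model without participants who were hospitalized to assess sensitivity of results". No time limit is put on the hospitalisation. SAP 2.5 carries similar approaches over to the nasal AUC.

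**Hospitalisation as an outcome.** Protocol 6.3 excludes "Patients who are hospitalized for inpatient treatment or currently being evaluated for potential hospitalization at the time of initiation of informed consent". Protocol 3.2 sets out to evaluate Lambda "in reducing the duration of symptoms, hospitalizations, or ED visits in patients with uncomplicated COVID-19 disease". SAP 1.3 lists as a secondary endpoint: "Number of emergency department visits or hospitalizations within 28 days of treatment".

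**Population and missing data.** SAP 2.1 states: "All efficacy analyses will be completed in the ITT population". SAP 3 assumes data are missing at random and promises sensitivity analyses for missingness, but gives a method only for time to shedding cessation. Protocol 9.1.2 says that at each clinic visit "oropharyngeal and anterior nare swabs will be collected".

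**The concern.** Because anyone in hospital or under evaluation for admission at consent is ineligible, every hospitalisation that triggers the exclusion happens after randomisation. It is also something Lambda is hoped to reduce. If admission is related to viral load and its frequency differs by arm, the refit removes more high-load participants from one arm than from the other. The groups left are no longer balanced by randomisation, and the AUC difference can move for that reason alone.

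The second issue is what the refit leaves unexamined. Oropharyngeal swabs are tied to clinic visits, so an admitted participant may well miss some, though the documents do not say what happens to swabs on admission. The open question is whether unobserved loads are higher than the imputation model predicts. Deleting people does not address it, and the SAP sets out no other analysis for the AUC that would.

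At stake is the reading of a supportive analysis of one secondary endpoint and, through SAP 2.5, of an exploratory one.

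**Working it through.** The plan states no figure that depends on this point, so there is nothing to reproduce. Two things were checked: how far the exclusion alone moves the estimate, and whether the refit reacts when missing at random fails.

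**Inputs.** From the documents: 60 per arm (SAP 1.1). Assumed, because the documents give neither: admission rates and the link between admission and load. Everything is in SD units of the analysed AUC, with differences taken as Lambda minus placebo, so a positive shift is against Lambda.

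**Yardstick.** With complete data, the standard error of the arm difference is √(2/60) = 0.183 SD.

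**Step 1: selection, logistic model.** Assume logit P(admission) = a + ln(3) × load + ln(OR) × arm. The admission odds triple per SD of load, and OR is Lambda's direct effect on admission. The constant a is set to give the control rate. The distortion is the arm difference among non-admitted participants minus the true difference, found by numerical integration.

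| True difference | Direct OR | Control v Lambda admitted | After exclusion | Distortion | Distortion / SE |
|---|---|---|---|---|---|
| -0.30 | 1 | 3.0% v 2.2% | -0.292 | 0.008 | 0.04 |
| -0.30 | 1 | 9.0% v 6.8% | -0.280 | 0.020 | 0.11 |
| -0.30 | 0.3 | 5.7% v 1.4% | -0.257 | 0.043 | 0.23 |
| -0.30 | 0.3 | 9.0% v 2.3% | -0.236 | 0.064 | 0.35 |
| 0 | 0.3 | 5.7% v 1.9% | +0.038 | 0.038 | 0.21 |
| 0 | 0.3 | 9.0% v 3.2% | +0.056 | 0.056 | 0.31 |
| 0 | 1 | equal | 0 | 0 | 0 |

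In the two null rows with OR 0.3, two-sided rejection at 5% rises to 5.5% and 6.1%.

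**Step 2: selection, a different model.** Let admission be a threshold on a normal variable correlated ρ with AUC, with no effect of Lambda on load. Excluding a fraction p shifts an arm's mean by -ρ × φ(z)/(1 - p), where z is the upper-p normal quantile.

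- At 10% v 2% with ρ = 0.4, the arm shifts are -0.4 × 0.195 = -0.078 and -0.4 × 0.049 = -0.020, so the spurious difference is +0.058.
- At 3.3% v 0%, ρ from 0.2 to 0.6 gives 0.015 to 0.046.
- The largest value on the grid tried, 0.099 (rejection 8.5%), needs 15% v 5% and ρ = 0.6.
- With ρ = 0 the result is zero at every pair of rates.

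**Step 3: does the refit respond when missing at random fails?** Suppose 10% to 20% of Lambda participants have a missing AUC that is truly 0.5 to 1.0 SD above what the imputation predicts. The true difference then runs from 0.10 × 0.5 = 0.05 to 0.20 × 1.0 = 0.20 SD. Simulation (400,000 per arm, ρ = 0.4, imputing within arm and admission status) gave:

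- main analysis: about 0.00 throughout;
- refit, 3.3% admitted in both arms: about 0.00 throughout, so the departure goes unseen;
- refit, 10% v 2% admitted: 0.054 to 0.062 whether the departure was absent or present, so the movement is selection only.

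**Step 4: timing.** The last load in the AUC is Day 14 and follow-up runs to Day 28. As written, a participant admitted on Day 20 with all seven swabs would be dropped.

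**The case against.** The strongest reply is that the SAP gives the purpose only as sensitivity of results. Read plainly, that is an influence check: does the answer depend on hospitalised participants and their imputed values? The refit does answer that. A reader might infer from its place after the imputation text that it was meant to test missing at random and fails at that job; the SAP does not say so. This part of the reply stands.

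A reader might also infer that it is the only missing-data check planned. SAP 3 promises missingness sensitivity analyses in general, so the fair statement is that no method is given for the AUC. The mixed model of the same loads in SAP 2.4 does not fill the gap, because it rests on the same assumption.

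Nor do the documents support calling this a breach of the ITT statement in SAP 2.1. The main AUC analysis keeps everyone in the assigned arm, and a supplementary refit does not replace it. The SAP simply does not label the refit as outside that population.

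Finally, a reader might expect the refit to make a real effect look fragile, or to mislead whatever happens. The figures do not bear that out: shifts of 0.04 to 0.35 of a standard error would seldom change a reading. The larger ones need a strong load link and a direct effect on admission together, and the spurious difference needs a drug that prevents admission without lowering load.

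What survives is narrower. The refit is not protected by randomisation, and it leaves the missing-data assumption where it was.

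**Conclusion.** The concern holds in a limited form. The one sensitivity analysis set out for the AUC conditions on a post-randomisation outcome that Lambda is intended to reduce, has no time limit matching the Day 14 window, and does not vary the missing-at-random assumption.

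The size is small: about 0.01 to 0.06 SD with 3% to 9% of controls admitted and odds tripling per SD of load, against a standard error of about 0.18 SD. More extreme assumed rates and correlations reach about 0.10 SD. It is zero if admission is unrelated to load, or if Lambda affects neither load nor admission. All of these rates and links are assumptions.

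No primary result and no main secondary estimate changes. This is a cheap improvement, not a flaw that threatens the trial's conclusions.

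**What to change.** In SAP 2.4, make the AUC sensitivity analysis a delta-adjusted (tipping-point) repeat of the pooled regression in all randomised participants:

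- Before the AUC is calculated, shift the imputed loads for all missing swabs by a range of fixed amounts (for example +1 and +2 log10, as illustrations only), first in both arms and then in the Lambda arm only.
- Show swabs missing after admission separately as well. They should not be the only ones shifted: the protocol synopsis assumes 90% complete follow-up, which leaves about 12 of 120 not completing, whereas 3% to 9% of 60 controls is about 2 to 5 people.
- Report the shift at which the conclusion changes, or state that none in the range changes it.
- If the exclusion of hospitalised participants is kept, label it descriptive and limit it to admissions by Day 14.
- Apply the same to the nasal AUC in SAP 2.5.

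The cost is a short SAP edit and a few extra runs on the five imputed data sets already planned. The downside is that the shift sizes need a justification, which the documents do not supply. The change would give the AUC the missingness sensitivity analysis that SAP 3 promises in general terms.

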5.2. Secondary efficacy endpoints

- SARS-CoV-2 RNA levels during follow-up
- SARS-CoV-2 viral load area under the curve
- Time to alleviation of all symptoms (fever, chills, cough, nasal congestion, muscle pains), defined as the time from initiation of treatment until all symptoms are rated as absent or mild in symptomatic patients
- Incidence of emergency department visits or hospitalizations within 28 days of initiation of treatment

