12.4 Analysis of secondary endpoints

SARS-CoV2 Log₁₀ viral loads at follow-up timepoints will be compared between groups using the Wilcoxon rank-sum test and/or generalized estimating equations with robust standard errors. The area-under-the-curve (AUC) SARS-CoV2 viral RNA levels during follow-up will be estimated using the linear trapezoidal method, and mean AUC levels compared between groups using the Wilcoxon rank-sum test.

The distribution of cessation of symptoms will be estimated using the Kaplan-Meier method, and Kaplan-Meier curves will be presented for each treatment arm. Time to cessation of symptoms at the end of the study period along with 95% confidence intervals will be presented for each treatment arm. The hazard ratio for cessation of symptoms will be estimated, along with its 95% confidence intervals, from a Cox proportional hazards model. Time to cessation of symptoms will be estimated in the subgroup of patients who are symptomatic at baseline.

The incidence of hospitalizations and emergency department visits will be compared between groups using negative binomial regression models, which will account for differing follow-up times through an offset term.

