## 2.5 Exploratory efficacy analyses

An alternative definition of the secondary endpoint of symptom resolution will be considered in an exploratory analysis. We will evaluate time to sustained symptom resolution, defined as time from randomization until the first day in which no symptoms are reported and are not reported for the duration of the study. The analysis of time to sustained symptom resolution will follow the methods described for the secondary endpoint evaluation symptom resolution in the previous section. Time to symptom resolution based on symptom subsets (i.e. respiratory, systemic) will be similarly analyzed, additionally excluding participants who did not report symptoms from the specified subset at screening.

Time to disease progression will be defined as the time from randomization until the first day of a two point or more increase in either cough or shortness of breath persisting for at least 48 hours or an increase to a score of 4 or 5, or first day of admission to the emergency department, hospitalization, or death. Analysis and reporting of results will be done following methods detailed for time to symptom resolution.

Freedom from SARS-CoV-2 infection by oropharyngeal and nasal swabs at Day 5, 7, 10, and 14 will be modeled using a multivariable logistic regression model adjusted for age and sex. The odds ratio will be presented along with its 95% confidence interval.

Similar approaches to those used for evaluating SARS-CoV-2 viral load in oropharyngeal tests over time and AUC will be used to evaluate viral load in nasal tests.

Correlation between virology and symptomology will be characterized by evaluating the relationship between CT values obtained from the oropharyngeal tests and each symptom through two main approaches. For symptoms graded on an ordinal scale, we will calculate a Spearman correlation and assess significance with a Z-test. For variables that capture presence of a symptom, differences in the median CT values by presence or absence of the symptom will be presented and assessed via a Wilcoxon rank sum test.

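### SAP 2.4 reports ED visits and hospitalizations by arm only, dropping the between-arm comparison in Protocol 12.4 without a stated reason

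*SAP*

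**What the plan says.** The objective in Protocol 3.2 is comparative: Lambda "compared with placebo, in reducing the duration of symptoms, hospitalizations, or ED visits in patients with uncomplicated COVID-19 disease". Protocol 5.2 lists the matching secondary efficacy endpoint as "Incidence of emergency department visits or hospitalizations within 28 days of initiation of treatment". SAP 1.3 lists it as "Number of emergency department visits or hospitalizations within 28 days of treatment".

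The two analysis sections differ:

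- Protocol 12.4: "The incidence of hospitalizations and emergency department visits will be compared between groups using negative binomial regression models", with an offset term for unequal follow-up.
- SAP 2.4: "The incidence of hospitalizations and emergency department visits will be estimated for each arm, with 95% confidence intervals". It names no contrast, model or test.

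SAP 2.5 also has an exploratory endpoint, time to disease progression. It combines worsening cough or shortness of breath with the "or first day of admission to the emergency department, hospitalization, or death", and is analysed by the methods used for symptom resolution.

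**The concern.** An objective that compares two arms needs an estimate of the difference between them. Two separate intervals do not supply one. A reader is left to judge by whether they overlap, which is not a test and gives no effect size.

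The gap is specific to this endpoint. In the SAP's other secondary analyses, symptom resolution has a hazard ratio, oropharyngeal viral load has an arm-by-time term, and viral load AUC has a difference with a 95% CI.

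The protocol does plan a comparison, so the two documents conflict and neither says which governs. If the SAP is followed, the report will have no direct Lambda-versus-placebo estimate for ED visits and hospitalizations. If a contrast is added later, its form will have been chosen after the data were seen.

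**Working it through.** The documents give no event rate, effect size or power for this endpoint, so there is no planned figure to reproduce. The main check compares the texts. The arithmetic after it is illustrative.

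**1. The texts side by side**

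| Item | Protocol | SAP |
|---|---|---|
| Endpoint | Incidence over 28 days (5.2) | Number over 28 days (1.3) |
| Analysis | Negative binomial between groups, with offset (12.4) | Incidence per arm with 95% CI (2.4) |
| Between-arm estimate | Yes | None |
| Reason for the change | n/a | None given |

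SAP 2.4 also does not say whether incidence means a rate per person-time or a proportion of participants. Even the per-arm interval is therefore not fully defined.

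**2. Would restoring the protocol model be enough?**

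Inputs: 60 per arm (SAP 1.1). Assumptions: placebo risk *p*, risk *p*/2 on Lambda, independent participants, complete follow-up.

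P(at least one arm has no participant with an event) = 1 − [1 − (1 − *p*)^60] × [1 − (1 − *p*/2)^60]

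| *p* | (1 − *p*)^60 | (1 − *p*/2)^60 | P |
|---|---|---|---|
| 1% | 0.547 | 0.740 | 88% |
| 2% | 0.298 | 0.547 | 68% |
| 3% | 0.161 | 0.404 | 50% |
| 5% | 0.046 | 0.219 | 25% |

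With no events in one arm the log rate ratio has no finite estimate. A log-link negative binomial fit (dispersion fixed at 1) to 0/60 versus 6/60 gave a log rate ratio of about −22 with a standard error of about 18,000.

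**3. What separate intervals can and cannot show**

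These are hypothetical splits, Lambda versus placebo. Per-arm intervals are Clopper-Pearson. The difference is placebo minus Lambda.

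- 0/60 vs 6/60: intervals 0 to 6.0% and 3.8 to 20.5%, which overlap. Risk difference 10 points, Newcombe 95% CI 2.0 to 20.1. Fisher p = 0.027.
- 1/60 vs 8/60: intervals 0.04 to 8.9% and 5.9 to 24.6%, which overlap. Fisher p = 0.032.

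These are the smallest splits that reach p < 0.05 from zero and from one event: 0 vs 5 gives p = 0.057 and 1 vs 7 gives p = 0.061. They show that overlap and a test can disagree, not that such results are likely.

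**4. Precision of a contrast**

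For a true rate ratio of 0.5, with expected events 60*p* and 30*p* and a Poisson approximation, the 95% CI is 0.5 × exp(±1.96 × √(1/(60*p*) + 1/(30*p*))).

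- *p* = 5%: 3 and 1.5 events, CI 0.07 to 3.55
- *p* = 10%: 6 and 3 events, CI 0.13 to 2.00
- *p* = 15%: 9 and 4.5 events, CI 0.16 to 1.55
- *p* = 20%: 12 and 6 events, CI 0.19 to 1.33

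Power of Fisher's test, summing binomial probabilities over all tables with p ≤ 0.05, is about 2%, 9%, 17% and 25% in the same order.

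**5. Interval and p-value together**

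At 0/60 vs 5/60 the Newcombe interval is 0.7 to 18.1 points and excludes zero, while Fisher p = 0.057. A plan that reports both must say which one governs.

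**The case against.** The strongest reply is that the comparison is already pre-specified, because Protocol 12.4 names the model and the offset. That is correct. A reader might infer that the objective goes unanswered in the plan as a whole, and the documents do not support that. The gap lies in the SAP and in the unresolved conflict between the two documents.

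A second reply is that the arms are compared on these events elsewhere. SAP 2.5 includes them in time to disease progression. SAP 2.6 compares adverse events by arm, and Protocol 10.1.3 makes inpatient hospitalization a criterion for a serious adverse event. It would therefore be wrong to call this endpoint the trial's only hard clinical efficacy measure. Neither route replaces the missing contrast, however. The first is exploratory and mixes in symptom scores. The second concerns safety, and an ED visit is not in itself a listed criterion.

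A third reply is that so few events are expected that a descriptive summary is sensible. That may be so, but the SAP does not say it, and the protocol still promises a comparison. Low power is a reason to show an effect with its wide interval, not to omit the effect.

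Finally, it is tempting to say that overlapping intervals would hide a real difference. The SAP does not propose overlap as a test, and the splits that show the problem are boundary cases with no support from a documented event rate.

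**Conclusion.** The point holds as a discrepancy between protocol and SAP. For a secondary endpoint with a comparative objective, SAP 2.4 replaces a planned between-group model with per-arm incidence and does not explain why. Analysis under the SAP gives no direct treatment effect for ED visits and hospitalizations.

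This rests on the text alone and is secure. The numbers rest on assumptions: 60 per arm, complete follow-up, and event risks that the documents do not give. On those assumptions, a zero-event arm is common at placebo risks of 1% to 5%, so the protocol model needs a fallback. At placebo risks of 5% to 20%, a halving would be estimated with an interval running from well below 0.5 to above 1. The loss is therefore an effect estimate and its uncertainty, not a difference the trial was likely to detect. The primary analysis is unaffected. The change should be made, but the trial's main conclusion does not depend on it.

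**What to change.** Add one between-arm estimate with a 95% CI to SAP 2.4, and align Protocol 12.4 with it. Either option is acceptable:

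1. **Rate ratio.** Carry over the protocol's negative binomial model with its follow-up offset. State in advance when it gives way to a fallback, for example when either arm has no events, the model fails to converge, or total events fall below a set minimum. The fallback is the risk difference in option 2.
2. **Risk difference.** Compare the proportion of participants with at least one ED visit or hospitalization by Day 28, with a Newcombe or a Miettinen-Nurminen 95% CI, chosen in advance. Report visit counts descriptively.

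Under either option:

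- State how participants lost before Day 28 are counted. The offset covers this in the rate model, but a proportion needs an explicit rule. The general multiple imputation statement in SAP 3 does not set one out for this endpoint.
- Name the CI as the basis for inference, so that it cannot conflict with a separate Fisher p-value.
- Use one endpoint definition, a count or a proportion, in Protocol 5.2 and SAP 1.3.
- Say whether the estimate is adjusted for age and sex, as the SAP's other secondary models are.

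The cost is wording in two documents and no new data. It should be done before the database is locked and the blind is broken (Protocol 8.2).
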